#### **Populations for Data Analysis**

The Intention-to-treat (ITT) population includes all patients who have received at least one dose of Vertigoheel® and have at least one post-baseline measurement.

As data collection will be based on routine clinical practice so that no stipulations will be made on assessments as well as on study visits, a PP population will not be defined. Protocol deviations (as far as known), e.g. deviations from the in-/exclusion criteria, will be listed.

The Safety population includes all patients who have received at least one dose of Vertigoheel®. Clinical safety will be addressed by assessing AEs, physical examinations, vital signs in a descriptive manner.

Effectiveness analyses will be performed with the ITT population, safety analyses with the Safety population.

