5.3.8 Safety

Safety data will be collected in this study.

Clinical safety will be addressed by assessing AEs, physical examinations and vital signs in a descriptive manner.

As AEs and relevant medical history will not be coded with MedDRA, they will not be grouped by MedDRA preferred terms.

As previous and concomitant medication will not be coded with the World Health Organization Drug Dictionary, they will not be grouped to the Anatomic Therapeutic Chemical index.

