5.5 Populations for Data Analysis

The Intention-to-treat (ITT) population includes all patients who have received at least one dose of Vertigoheel® and have at least one post-baseline measurement.

As data collection will be based on routine clinical practice so that no stipulations will be made on assessments as well as on study visits, a per-protocol population will not be defined. Protocol deviations (as far as known), e.g. deviations from the in-/exclusion criteria, will be listed.

The Safety population (SP) includes all patients who have received at least one dose of Vertigoheel®.

Effectiveness analyses will be performed with the ITT population, safety analyses with the Safety population.

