Appendix 1: Tables, Listings, Figures

Item No.	Title	Population	Content Description
14.1	Disposition, Baseline Characteristics, Medication and Further Analyses		
14.1.1	Patient disposition	All	Descriptive statistics on patients screened, failed screening, treated
14.1.2	Early termination	All	Descriptive statistics for early termination yes/no
14.1.3	Number of patients in each analysis population	All	Descriptive statistics for number and percentage of patients and reason for exclusion
14.1.4	Duration of study	All	Date of first patient in and last patient out of all patients
14.1.5	Duration of observation per patient	SP	Difference of Date of patient in and patient out per patient
14.1.6	Demographics and other baseline characteristics	ITT	Descriptive statistics of age, , height, weight, pregnancy test
14.1.7.1	Vital signs	ITT	Descriptive statistics of heart rate and blood pressure, at Screening Visit and 2±1 month after baseline
14.1.7.2	Physical examination	ITT	Descriptive statistics (normal, abnormal, ncs (not clinically significant), cs (clinically significant)), at Screening Visit and 2±1 month after baseline (shift table)
14.1.8.1	Primary diagnosis	ITT	Descriptive statistics of 
 - FD yes/no (derived from tick box 'NA' for caloric (BVP)) - BVP yes/no (derived from tick box 'NA' for GAD-7 (FD))
14.1.8.2	Medical history - Abuse history	ITT	Descriptive statistics of alcohol and drug consumption, smoking status
14.1.9.1	Treatment with Vertigoheel	SP	Descriptive statistics for 
 - Duration of treatment (date start of study – date start of Vertigoheel treatment - change of Vertigoheel dose yes/no
14.1.9.2	Prior medication	SP	Descriptive statistics for prior medication yes/no
14.1.9.2	Concomitant medication	SP	Descriptive statistics for change of concomitant medication yes/no
14.1.9.3	Product complaints	SP	Descriptive statistics for product complaint yes/no

14.2	Patient Reported Outcomes (Effectiveness)		
14.2.1	Primary Endpoint		
14.2.1	Dizziness Handicap Inventory	ITT	Descriptive statistics at Screening Visit and 2±1 month after baseline (yes, sometimes, no), and change from baseline to 2 months (shift table)
14.2.2	Secondary Endpoints		
14.2.2.1	Posturography	ITT	Descriptive statistics at Screening Visit and 2±1 month after baseline (normal, neuritis vestibularis, PPV), and change from baseline to 2±1 month after baseline (shift table)

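### Vital signs and physical examination are classed as safety, but their tables are assigned to the ITT set while the adverse-event table uses the Safety population

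*SAP*

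**What the plan says.** SAP 5.3.8 defines what counts as safety: "Clinical safety will be addressed by assessing AEs, physical examinations and vital signs in a descriptive manner". The protocol says the same under Populations for Data Analysis: "Clinical safety will be addressed by assessing AEs, physical examinations, vital signs in a descriptive manner". The protocol summary also lists physical examination and vital signs among its safety observations.

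SAP 5.5 then links type of analysis to population: "Effectiveness analyses will be performed with the ITT population, safety analyses with the Safety population". The two sets differ by one condition. For safety: "The Safety population (SP) includes all patients who have received at least one dose of Vertigoheel". ITT patients must "have received at least one dose of Vertigoheel® and have at least one post-baseline measurement".

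SAP Appendix 1 labels both of these tables ITT:

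- Table 14.1.7.1, vital signs: "Descriptive statistics of heart rate and blood pressure, at Screening Visit and 2±1 month after baseline".
- Table 14.1.7.2, physical examination: "Descriptive statistics (normal, abnormal, ncs (not clinically significant), cs (clinically significant)), at Screening Visit and 2±1 month after baseline (shift table").

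The adverse-event overview, Table 14.3.1.1, is labelled SP. Appendix 1 lists no other vital-sign or examination table.

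**The concern.** The SAP states a rule and its table list departs from it for two of the three components of clinical safety. A treated patient with no post-baseline measurement is counted in the adverse-event table and is absent from the other two. The denominators differ as well, because SAP 5.4 bases percentages on the size of the analysis population. A reader who sets adverse events beside vital signs and examination findings would be comparing different groups of patients, and the table titles would not explain why.

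**Working it through.** **Step 1: is this a contradiction, or a deliberate choice?** Two explanations could make the ITT label intentional.

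- *The tables are baseline tables.* They sit under heading 14.1, which covers disposition, baseline characteristics and medication. But both report the follow-up visit, and 14.1.7.2 is a shift table.
- *Everything under 14.1 is on ITT.* It is not. Table 14.1.5 and the 14.1.9 tables, under the same heading, are on SP.

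Neither explanation holds, so the labels conflict with SAP 5.5.

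**Step 2: how many patients could be affected?** The plan gives no figure to reproduce. The inputs are:

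- Planned enrolment: 20 patients with bilateral vestibulopathy (BVP) and 40 with functional dizziness (FD), 60 in all (SAP 5.4; protocol Section 8).
- Loss to follow-up, first source: 10% (SAP 5.1; protocol Section 8).
- Loss to follow-up, second source: 10% in BVP and 20% to 30% in FD (protocol summary, Statistical Methods).

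The assumptions are that all 60 are dosed, that every lost patient has no post-baseline measurement, and that none is replaced. Then

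patients in SP but not in ITT = 20 × (BVP loss) + 40 × (FD loss).

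| Loss, BVP / FD | Left out | ITT size | Share of 60 |
|---|---|---|---|
| 10% / 10% | 2 + 4 = 6 | 54 | 10% |
| 10% / 20% | 2 + 8 = 10 | 50 | 17% |
| 10% / 30% | 2 + 12 = 14 | 46 | 23% |

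**Step 3: what would be missing from the tables?** This depends on what a post-baseline measurement is, which neither document defines.

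- *Any measurement.* A patient with even one follow-up vital sign is in ITT. Those outside ITT have no follow-up values to show, and SAP 5.4 rules out imputation. The label then affects only their baseline values and the denominators.
- *An effectiveness measurement only.* A patient seen after baseline only for a safety check, for example at an unscheduled visit (protocol 6.6), would be outside ITT, and those follow-up safety values would not be tabulated.

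**Step 4: does relabelling alone suffice?** Take, for illustration, 3 patients with an abnormal follow-up examination. Under the SAP 5.4 denominator:

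- ITT of 46: 3/46 = 6.5%
- ITT of 50: 3/50 = 6.0%
- ITT of 54: 3/54 = 5.6%
- SP of 60: 3/60 = 5.0%

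Moving the tables to SP and changing nothing else would lower the follow-up percentage by adding patients who were never re-examined. The denominator has to be dealt with at the same time.

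**The case against.** The strongest reply is that this is a labelling slip with little effect on safety findings. A reader might infer that the safety results of patients who leave early are being discarded. The documents do not support that as it stands, for three reasons.

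- The ITT definition does not restrict the kind of measurement. The heading of SAP 5.3 pairs effectiveness endpoints with measurements, but Safety (5.3.8) is one of its subsections, and protocol Section 4, Measurements, likewise contains 4.8 Safety. The heading therefore gives no good ground for the narrow reading.
- Protocol 6.4 asks that the activities of the final visit be carried out when a patient discontinues. These include the Dizziness Handicap Inventory (DHI), EQ-5D-5L and posturography. A patient handled this way has effectiveness data and is in ITT on either reading.
- Adverse events of all treated patients are tabulated on SP in any case.

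It can also be said that 10 to 14 patients should not be quoted alone, since the SAP's own loss rate gives 6. Further, Table 14.1.3 will show the population sizes and reasons for exclusion, and SAP 5.4 already reports the number of observations for continuous variables, which covers vital signs.

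All of this stands, and it limits the consequence. It does not remove the conflict between SAP 5.5 and the two labels, and it leaves the meaning of a post-baseline measurement open.

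**Conclusion.** The inconsistency is real and present in the current text; its effect is minor. The figures of 6, or 10 to 14, of 60 are upper limits under the assumptions in the working. Final-visit assessments at discontinuation would reduce them. Replacement of non-completers, which protocol 3.2 allows, would change the counts and shares but would not bring the excluded patients back into ITT.

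On the plain reading of the ITT definition, what changes is mainly the baseline summaries and the denominators. Loss of post-baseline safety values follows only from the narrower reading, which the documents do not require. The analysis is descriptive, so no test, error rate or sample size is affected.

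**What to change.** 1. In SAP Appendix 1, change the population of Tables 14.1.7.1 and 14.1.7.2 from ITT to SP.
2. For follow-up and shift-table percentages, use as denominator the patients with both a baseline and a post-baseline value, and print that number. State this in SAP 5.4 as an exception to the analysis-population denominator.
3. Align the description of Table 14.1.7.2, which names only the screening and 2±1 month assessments, with SAP 5.4, under which the physical-examination shift table uses the worst category after baseline. Say that unscheduled and early-termination values count.

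The cost is two labels, one reworded table description and a small exception to the stated denominator rule. No new data are needed. Item 2 should not be left out, since relabelling alone dilutes the follow-up percentages.

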	sensation of vertigo and dizziness as change from baseline
	to month $2\pm 1$ assessed by the Dizziness Handicap
	Inventory (DHI; total).
Secondary Endpoints	• Effect of Vertigoheel ® on QoL as change from baseline to
	month $2\pm 1$ assessed by EQ-5D-5L.
	• Effect of Vertigoheel ® on total sway path as change from
	baseline to month $2\pm 1$ assessed by static posturography.
	• In FD effect of Vertigoheel ® on psychiatric symptoms as
	change from baseline to month $2\pm 1$ assessed by Patient
	Health Ouestionnaire Mood Scale (PHO-9) and
	Generalized Anxiety Disorder Screener (GAD-7)
	• In BVP effect of Vertigoheel ® on vestibular function as
	change from baseline to month 2+1 assessed by video
	head impulse test (vHIT) and/or caloric testing
	• Adverse events (AFs)
	
 
Other observations related to safety (physical examination)
 

	and vital signs)
Study Design	Non-interventional observational prospective monocentric
Study Design	study
Study Population	It is planned to include 20 patients with BVP and 40 patients
	with ED who are going to start Vertigoheel ® treatment
	according to clinical practice at the study conter
	The desision of treatment is up to the physician's discretion
	The decision of treatment is up to the physician's discretion
Inclusion / Evolusion	and is to be made independent of this study.
Criteria	Following documentation criteria should be fulfilled
Cintoina	• BVP (according to the diagnostic criteria of the Bárány
	Society) or FD (according to the diagnostic criteria of the
	Bárány Society).
	• Symptoms for > 3 months of moderate to severe intensity
	according to the DHI [0 (minimum score) -100 (maximum
	score)] of 30 to 90 points.
	• $\geq 18 - 80$ years of age.
	• Legally competent male or female outpatient.
	Signed informed consent.
	• Not pregnant (as proven by negative pregnancy test in
	case of woman of childbearing potential before first
	study drug administration) or breast-feeding.
	Patients with the following conditions are excluded from the
	documentation in this NIS
	• Ongoing (within the last two months) or recently started
	Vertigoheel ® treatment.
	• Debilitating acute or chronic illness (e.g. psychiatric
1	
	illnesses).

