FD is another general term for somatoform or psychogenic dizziness with some subtypes such as "Persistent Postural-Perceptual Dizziness". The prevalence of FD as a primary cause of vestibular symptoms amounts to 10% in neuro-otology centers. Rates of psychiatric comorbidity in patients with structural vestibular syndromes are much higher with nearly 50% and with highest rates in patients with vestibular migraine, vestibular paroxysmia and Ménière's disease. Pathophysiologic processes seem to include precipitating events that trigger anxiety-related changes in postural strategies with an increased attention to head and body motion and a co-contraction of leg muscles. FD can be determined by normal results in the neurological tests. Treatment plans include patient education, vestibular rehabilitation, cognitive behavioral therapies, and medications substantially reducing morbidity and offering the potential for sustained remission when applied systematically.

According to German law for this observational study only patients are eligible for whom the treating physician has decided to start treatment with Vertigoheel® independently from the study and in agreement with the patient. It is neither allowed nor the intention to motivate any interventions in the patients' treatment by conduction of this study.

Regardless of the exact cause of vertigo attacks, it is important to reduce the frequency, intensity,

Product: Vertigoheel Observational Plan Version: 1 – 15JULY2021

and duration of vertigo attacks with an effective medication that has minimal side effects. Vertigoheel® is a natural medicinal product containing four measurable active ingredients for the treatment of vertigo. Vertigoheel® tablets were approved by BfArM as treatment for vertigo of various origins. The efficacy and safety evaluation of Vertigoheel® versus betahistine hydrochloride demonstrated a reduction of 2 score points of the mean intensity of vertigo attacks with a standard deviation of 0.8 score points and a non-inferiority limit of 20% (Weiser et al 1998).

*Legal and regulatory aspects of non-interventional studies in Germany* Stringent requirements for non-interventional studies exist in Germany that will all be adhered to in this NIS:

- Regulatory recommendations of the German Federal Institute for Drugs and Medical Devices (BfArM).
- Art. 2 of EU Directive 2001/20/EC.

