### **1.2 RATIONALE**

No systematic data in bilateral vestibulopathy and functional dizziness is available for Vertigoheel® regarding PRO and QoL in a real life setting in Germany. Nowadays, German health insurance is not only interested in direct costs, e.g. hospitalization, but also in patient reported and in clinical practice implemented outcome parameters. Therefore, patient-reported outcomes (PRO) as well as quality of life (OoL) assessed during clinical practice, were chosen as primary and secondary objectives respectively, to evaluate symptoms and QoL of Vertigoheel® treated patients in Germany. The current German AWMF guidelines for vestibular disorders (03/2021) recommend furthermore VOR, caloric testing, DHI and static posturography, as examinations for diagnosis and monitoring of the development for

patients with vertigo or dizziness.

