### **3.4 INCLUSION CRITERIA**

Patients will be included in the study if they meet all the following criteria:

- Treatment with Vertigoheel® has been chosen by the physician independently of including the patient in this non-interventional study.
- BVP (according to the current diagnostic criteria of the Bárány Society, 2017) or FD (according to the diagnostic criteria of the Bárány Society, 2017)
- Symptoms for > 3 months of moderate to severe intensity according to the DHI [0 (minimum score) -100 (maximum score)] between 30 to 90 points.
- $\geq 18 80$  years of age.
- Legally competent male or female outpatient.
- Signed informed consent.

• Not pregnant (as proven by negative pregnancy test in case of woman of childbearing potential before first study drug administration) or breast-feeding.

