## 4 MEASUREMENTS

Since this is a non-interventional study, no stipulations will be made on assessments as well as on study visits. Data collection will be based on routine clinical practice and no testing/evaluations will be done specifically for this protocol.

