3.4 Inclusion Criteria

Patients are included in the study if they meet all the following criteria

- Treatment with Vertigoheel® has been chosen by the physician independently of including the patient in this non-interventional study.
- BVP or FD (according to the current diagnostic criteria of the Bárány Society (2017)-FD
- Symptoms for > 3 months of moderate to severe intensity according to the DHI [0 (minimum score) -100 (maximum score)] of 30 to 90 points.
- ≥18 – 80 years of age
- Legally competent male or female outpatient
- Signed informed consent
- Not pregnant (as proven by negative pregnancy test in case of woman of childbearing potential before first study drug administration) or breast-feeding

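### The SAP derives FD and BVP from two separate 'NA' tick boxes rather than from the qualifying diagnosis, so a patient can be coded as both or neither

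*SAP*

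**What the plan says.** Both documents admit patients on a diagnosis. Protocol section 3.4 requires "BVP (according to the current diagnostic criteria of the Bárány Society, 2017) or FD", and SAP section 3.4 requires "BVP or FD (according to the current diagnostic criteria of the Bárány Society".

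SAP Appendix 1, Table 14.1.8.1, reports the primary diagnosis from other data. One line is "FD yes/no (derived from tick box 'NA' for caloric (BVP" and the other is "BVP yes/no (derived from tick box 'NA' for GAD-7 (FD". FD is therefore inferred from a caloric form marked not applicable, and BVP from a GAD-7 form marked not applicable. The table does not say which visit's box counts, although both assessments are scheduled at both visits.

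SAP section 5.4 names FD and BVP as the only subgroups and gives no derivation for them. Tables 14.2.2.3 and 14.2.2.4 (PHQ-9, GAD-7) are restricted to FD patients, and Tables 14.2.2.5 and 14.2.2.6 (vHIT, caloric) to BVP patients, again without a rule.

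**The concern.** The rule gives the right answer only if each 'NA' box is ticked strictly by diagnosis. Neither document says that it is, and two departures are plausible from the text, both through the caloric box.

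- **BVP without a caloric test.** The protocol summary lets vestibular function in BVP be assessed by "head impulse test (vHIT) and/or caloric testing", and Protocol section 4 says that "no stipulations will be made on assessments as well as on study visits". Caloric testing also requires that an eardrum lesion be excluded first (Protocol section 4.7). The vHIT table has a category for a test not done. The caloric table shows none, so how an omitted caloric test is recorded is unknown. If it is recorded as 'NA', the patient is coded as both.
- **FD with a caloric test.** Protocol section 1.1 states that "FD can be determined by normal results in the neurological tests". Section 1.2 cites a guideline that recommends "caloric testing, DHI and static posturography, as examinations for diagnosis and monitoring of the development for" patients with vertigo or dizziness in general. If such a caloric result is entered in the CRF, the patient is coded as neither.

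At stake are the counts in Table 14.1.8.1 and, if the same flags are used elsewhere, membership of the two subgroups and of the FD-only and BVP-only tables. An FD patient coded neither would leave the PHQ-9 and GAD-7 tables although both scores exist. A BVP patient coded both would add to the FD count without supplying a GAD-7 value.

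**Working it through.** **Inputs.** The rule is FD = caloric 'NA' and BVP = GAD-7 'NA' (SAP Table 14.1.8.1). The planned sizes are 40 FD and 20 BVP (SAP section 5.4). The documents give no error rate, so k = 2, 4 or 6 affected patients is an assumption. All 60 patients are taken to be in the ITT population, with every other box ticked as intended. The plan gives no figure on this point to reproduce.

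**All combinations of the two boxes**

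| Caloric 'NA' | GAD-7 'NA' | Coded as |
|---|---|---|
| yes | no | FD only |
| no | yes | BVP only |
| yes | yes | both |
| no | no | neither |

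A BVP patient (GAD-7 'NA' ticked) whose caloric box is also ticked moves from the second row to the third. An FD patient (GAD-7 completed) whose caloric box is not ticked moves from the first row to the fourth.

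**Case 1: k BVP patients coded both.** FD = 40 + k, BVP stays 20, the sum is 60 + k, and the share of BVP patients in 'FD' is k/(40 + k).

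| k | FD | Sum of flags (60 patients) | BVP share of 'FD' |
|---|---|---|---|
| 2 | 42 | 62 | 2/42 = 4.8% |
| 4 | 44 | 64 | 4/44 = 9.1% |
| 6 | 46 | 66 | 6/46 = 13.0% |

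**Case 2: k FD patients coded neither.** FD = 40 − k, the sum is 60 − k, and the share of FD patients lost is k/40. The 95% CI half-width in SD units is t(0.975, n − 1)/√n, which is 0.3198 at n = 40.

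| k | FD (n) | Sum of flags (60 patients) | FD lost | Half-width (SD units) | Ratio to n = 40 |
|---|---|---|---|---|---|
| 2 | 38 | 58 | 5% | 0.3287 | 1.028 |
| 4 | 36 | 56 | 10% | 0.3384 | 1.058 |
| 6 | 34 | 54 | 15% | 0.3489 | 1.091 |

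**Both errors with equal k.** FD = 40 − k + k = 40, BVP = 20 and the sum is 60. The totals match the plan, yet k/40 = 5%, 10% or 15% of 'FD' would be BVP patients. The totals in Table 14.1.8.1 would not show it.

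**The case against.** The strongest reply is that 'NA' most naturally means that the form does not apply to this diagnosis. The boxes carry the labels BVP and FD, both flow charts schedule the modules by diagnosis, and the text introduces them the same way. On that reading the box is a sound proxy. Protocol section 1.1 also includes a reduced or absent caloric response in the diagnosis of BVP, so a BVP patient with no baseline caloric test should be less common than the and/or wording suggests. An FD patient's caloric result may stay in the source record and never reach the CRF. Only one count table is documented as using the rule. Finally, Protocol section 9 provides consistency checks and queries, and at one centre with about 60 patients a conflict can be settled from source.

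Much of this stands. The intended meaning of 'NA' is probably as described, the pCRF could confirm it, and the wider use of the flags is an inference. Unequal errors would show, because the flags would not add up to the ITT total. Even with equal errors the GAD-7 table would report n = 40 − k beside an FD count of 40, although that could pass for ordinary missing data.

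It does not remove the defect. No text ties the boxes to diagnosis. The checks in section 9 are general, with the programmed ones left to a separate validation plan. The SAP still has no rule for a patient coded as both or neither.

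**Conclusion.** The concern holds as a conditional, low-impact defect. The stated rule can misclassify patients whom the eligibility diagnosis would classify correctly, and conflicts have no stated resolution. The size of the effect is unknown without the pCRF; the counts of 2, 4 and 6 show scale and are not estimates. The effect on Table 14.1.8.1 follows directly from the rule. The effect on the subgroups and on the FD-only and BVP-only tables assumes that the same flags are used there, which is likely because the SAP offers no other derivation. The study is descriptive, at one centre and without hypothesis tests, so the harm is confined to wrong group counts, some mixing of the two disorders and lost FD data.

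**What to change.** Define one mutually exclusive variable, indication (FD or BVP), from the Bárány diagnosis at Visit 0. If the pCRF has no field that separates the two, take it from the source record. Use it for Table 14.1.8.1, the section 5.4 subgroups and every table restricted to FD or BVP patients. Being both or neither is then impossible by construction, whatever tests were done. Keep the 'NA' boxes only as a consistency check: cross-tabulate them per patient against the indication and query discrepancies before database lock.

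The cost is a change of SAP wording and, at most, one source-verified item for about 60 patients at one site.

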#### Data Analysis

SAS or R software, or an equivalent software package will be used for statistical analysis.

Descriptive statistics will be provided for all parameters. The statistics will be appropriate for the type of data:

- For continuous and count variables, statistics will include the number of observations, mean, standard deviation, median, minimum, maximum, and 95% confidence interval (CI).
- For categorical variables, the descriptive statistics will include the count and percent of observations in each category along with its 95% CI. The denominator for the percentages will also be presented as the number of subjects in the analysis population.

This is a non-interventional, observational study, therefore only CI are calculated. If data transformations are used, they will be specified in the final clinical study report. All endpoints will be analyzed by the appropriate type of descriptive statistic(s) as described above.

All variables will be analyzed in an exploratory manner. No formal statistical hypothesis testing will be performed.

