5.4 Data Analysis

SAS or R software, or an equivalent software package will be used for statistical analysis.

Descriptive statistics will be provided for all parameters. The statistics will be appropriate for the type of data:

- For continuous and count variables, statistics will include the number of observations, mean, standard deviation, median, minimum, maximum, and two-sided 95% confidence interval (CI).

- For categorical variables, the descriptive statistics will include the count and percent of observations in each category along with its Clopper-Pearson two-sided 95% CI. The denominator for the percentage calculation will be based on the number of patients in the analysis population.

This is a non-interventional, observational study, therefore only CI are calculated. All endpoints will be analyzed by the appropriate type of descriptive statistic(s) as described above.

All variables will be analyzed in an exploratory manner. No formal statistical hypothesis testing will be performed.

Missing values will not be imputed.

The following subgroups will be defined:

- Patients with FD
- Patients with BVP

It is planned to include 20 patients with BVP and 40 patients with FD.

No further subgroups will be defined.

Shift tables for physical examination, DHI, Posturography, and vHIT will display the number and percentage of patients per baseline value category vs. the worst value category post-baseline

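### The SAP's effectiveness tables do not report the protocol's primary endpoint, change in DHI total, or the secondary endpoint, change in total sway path

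*SAP*

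**What the plan says.** **Protocol endpoints.** The Observational Plan Summary gives the primary endpoint as change from baseline to month 2±1 on the Dizziness Handicap "Inventory (DHI; total"). Among the secondary endpoints is the effect "on total sway path as change from" baseline, measured by static posturography.

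**SAP tables.** Appendix 1 has one DHI table, item 14.2.1, under a Primary Endpoint heading: "Descriptive statistics at Screening Visit and 2±1 month after baseline (yes, sometimes, no), and change from baseline to 2 months (shift table"). It has one posturography table, item 14.2.2.1, with the categories "normal, neuritis vestibularis, PPV), and change from baseline to 2±1 month after baseline (shift table"). SAP 5.4 repeats the choice: "Shift tables for physical examination, DHI, Posturography, and vHIT will display the number and percentage of patients per baseline value category", set against the worst category after baseline.

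**General rules.** Protocol section 8, Data Analysis, says: "For continuous and count variables, statistics will include the number of observations, mean, standard deviation, median, minimum, maximum, and 95% confidence interval (CI"). It adds: "All endpoints will be analyzed by the appropriate type of descriptive statistic(s) as described above". SAP 5.4 carries both rules over, and SAP 5.6.2 defines change as a numeric difference.

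**Definitions.** SAP 5.3.1 describes the DHI as 25 items in three sub-domains and gives no scoring. SAP 5.3.2 names no posturography parameter. SAP 5.3 says primary and secondary endpoints are not distinguished, but Appendix 1 uses both headings. On incomplete data, SAP 5.4 says only: "Missing values will not be imputed".

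**The concern.** The primary endpoint is one number per patient, a change on a 0 to 100 scale. The table under the primary heading instead shows counts of item responses and their shifts. The posturography table likewise replaces a measured length with a diagnostic pattern.

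An analyst working from the general rules and one working from the table list would deliver different primary results. The second would report no mean paired change and no CI for DHI total in either diagnosis. In a descriptive study with no hypothesis test, the estimate and its interval are the main product. They are also what the sample-size section is built on.

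**Working it through.** **1. Endpoint against table**

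| Measure | Protocol or general rule | SAP Appendix 1 |
|---|---|---|
| DHI | change in total score | item responses in three categories, shift table |
| Posturography | change in total sway path | three pattern categories, shift table |
| PHQ-9, GAD-7 | change (FD only) | total score at both visits, and change |

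The SAP names a total score for PHQ-9 and GAD-7 and gives those rows no shift table. It does not do so for the primary endpoint. Sway path appears nowhere in the SAP. The effectiveness block runs without a gap from 14.2.1 to 14.2.2.6 and both rows are readable, so text extraction does not explain the omission.

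**2. What the listed DHI table can show**

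Yes, sometimes and no are answers to single items, so the shifts describe items, not patients' totals. With complete data and known item scores, the mean change in total could be rebuilt by adding the item means. Its CI could not, because that needs the covariances between item changes.

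**3. The plan's sizing figure**

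Inputs from SAP 5.1: two-sided 95% CI, SD 0.8, n=20.

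- Half-width = 1.96 × 0.8 / √20 = 0.351, as stated.
- In SD units: 0.351 / 0.8 = 0.44.

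This is the half-width of a mean paired difference, the type of estimate that no listed table gives for DHI total.

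**4. Precision the general rules would give**

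The documents give no SD for change in DHI or sway path, so the half-width is in SD of the change: t(0.975, n−1) / √n.

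| Diagnosis | Loss | n | Half-width (SD) |
|---|---|---|---|
| BVP | none | 20 | 0.468 |
| BVP | 10% | 20 × 0.9 = 18 | 0.497 |
| FD | none | 40 | 0.320 |
| FD | 10% | 40 × 0.9 = 36 | 0.338 |
| FD | 20% | 40 × 0.8 = 32 | 0.361 |
| FD | 30% | 40 × 0.7 = 28 | 0.388 |

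The 10% loss is in protocol section 8 and SAP 5.1. The protocol summary gives 10% for BVP and 20% to 30% for FD. The rows with loss assume no replacement, although protocol 3.2 allows it. At n=20 the t value (0.468) exceeds the plan's 0.44 because the plan used the normal quantile.

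**5. DHI scoring**

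SAP 3.4 gives a range of 0 to 100 and SAP 5.3.1 gives 25 items. With equal weights each item carries up to 100 / 25 = 4 points. The score for the middle response is not stated. If a missing item were summed as zero, that total would fall by up to 4 points. If an incomplete total were set to missing, the patient would leave the change analysis.

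**The case against.** The strongest reply is that nothing is excluded. SAP 5.4 requires a mean and CI for continuous variables and extends suitable statistics to every endpoint. SAP 5.6.2 defines a numeric change, and item 14.2.1 itself asks for descriptive statistics and change from baseline. On that reading the shift table is an addition and the fault is a thin table description.

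It is true that the SAP nowhere says the analysis will be left out. But the general rule works by type of variable, and the SAP lists the DHI only by response category. With no total defined, the continuous rule has no DHI variable to act on.

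Four smaller points stand in part:

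- Scoring a missing item as zero sits badly with the no-imputation statement, so setting an incomplete total to missing is the more natural reading. The rule is still not written down.
- The half-widths show what the general rules would deliver. They do not measure the defect.
- The link to the sample size is to the type of statistic. SAP 5.1 names no endpoint, and 0.8 matches the SD that the protocol cites for vertigo-attack intensity in an earlier trial against betahistine, not an SD for the DHI.
- Sway path is one secondary endpoint and would merit a lower grade by itself. The mismatch in endpoint labels alters no estimate.

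**Conclusion.** The concern holds. The general rules and the specific tables conflict, and as listed the tables omit four estimates: mean change with 95% CI for DHI total and for sway path, each in FD and BVP. The need to fix this rests on DHI total alone, because it is the primary endpoint.

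The mismatch is read directly from the text and needs no assumption about variability. The half-widths assume a t interval and the stated losses without replacement. The figure of 4 points per item assumes equal weights. The CRF cited in the SAP introduction was not available, so whether sway path is captured as a number is unknown.

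**What to change.** **Item 14.2.1.** Add DHI total, the sum of the 25 items on 0 to 100, at baseline and Visit 1. State the score of each response and a rule for missing items. Add the change, Visit 1 minus baseline, with n, mean, SD, median, minimum, maximum and two-sided 95% CI, separately for the FD and BVP subgroups already defined in SAP 5.4. Keep the category and shift tables as supportive.

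**Item 14.2.2.1.** Add the same summary for total sway path if the numeric value is in the CRF or source records. If it is not, state in the SAP that this protocol endpoint cannot be reported.

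**Wording.** Name both variables in SAP 5.3.1 and 5.3.2, and align SAP 5.3 with the endpoint headings in Appendix 1.

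**Cost.** SAP wording and two table shells. Eligibility already requires a baseline DHI score of 30 to 90, and the Visit 1 total can be derived if item responses or the total are captured. The cost of obtaining sway path cannot be judged without the CRF.
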